#### **7.4.4 Blinding of Study Device**

Injections of the study device are performed by the unblinded Treating Investigator. The blinded Evaluating Investigator is not allowed to retrieve study supplies or to be present during opening of the study supplies or during the injections. The Treating Investigator is not to have any discussion with the Evaluating Investigator or subjects regarding the treatments.

Subjects are blinded to treatment assignment. Subjects are physically masked (blindfolded) just prior to and during all injection procedures to prevent observation of the syringes containing study device.

Subjects, investigators, the Sponsor's staff conducting the study, and members of the administrative team will not have access to individual subjects' treatment assignments. In the event of an emergency that requires breaking of the study blind, the randomization code will be maintained by each investigator that can be opened to reveal the study device.

See Section 7.9.10.2 for a description of the method of unblinding a subject during the study if such action is warranted.

At Visit 5, subjects and blinded evaluating investigators will be asked which treatment they thought was administered as a way of evaluating the blinding.

#### **7.4.5 Method of Packaging, Labeling, Storage, and Dispensing**

For PN40082, one 1.0 mL syringe is packaged along with two fine-gauge needles (30G) in an easy-open tray. Each syringe is equipped with a Luer-Lok as well as a custom finger grip and plunger rod. The syringes contain a peelable label to be placed on the subject record for tracking purposes. Two trays are packaged in a carton. A label that includes the protocol number and Sponsor name will be attached to each carton.

Restylane Silk study device will be supplied by Prolenium in the commercial packaging. Investigators will be instructed to follow instructions regarding storage in accordance with the study device's Directions for Use.

All study device will be stored in a climate-controlled, limited access area.

The investigator agrees to store and administer the study device only at the site(s) listed on Form FDA 1572 (or investigator agreement/statement). The investigator, sub-investigator(s), or qualified designees also agree that the study device will be administered only to subjects who have provided written informed consent and have met all entry criteria. Study device may not be used for any purpose other than as stated in the protocol.

#### **7.4.6 Study Device Accountability**

Study device will be available on site for each subject. Receipt of study device will be documented and confirmed via the Investigational Product Receipt Form. All study device must be kept in a locked area with access restricted to designated study personnel in a climate-controlled, limited access area. The administration of study device will be recorded on the Study Device Dispensing Log. The site monitor will periodically check the supply of study device held by the investigator or pharmacist to ensure accountability. At study conclusion, all unused PN40082 study device will be returned to the Sponsor and documented using the Investigational Product Return Form.

Inventory records must be readily available for inspection by the study monitor and/or auditor, and open to inspection by regulatory authorities at any time.

#### **7.4.7 Prior and Concomitant Medications**

All medications and other treatments taken by the subject within 6 months before Visit 1/Day 1 and during the study are to be recorded on the CRF using their generic name, if known, with the corresponding indication. The medications to be recorded include prescription and OTC medications and dietary supplements. All medications taken on a regular basis, including vitamins, aspirin, and acetaminophen, should be recorded prior to first use of the study device.

The use of any concomitant medication must relate to the subject's documented medical history, prophylaxis, or an AE.

##### **7.4.7.1 Precautions**

Subjects should be given the following additional instructions:

- Subject should minimize or avoid excessive natural or artificial sunlight exposure and extreme cold weather
- Subjects should avoid epilation, laser, mechanical or chemical peeling procedures during the study

##### **7.4.7.2 Medications and Treatments Prohibited Before Study Entry and During the Study**

The medications prohibited prior to Visit 1/Day 1 are listed in the exclusion criteria (Section 7.3.2).

Subjects will be advised to avoid the following for the duration of the study:

- Facial plastic surgery or permanent facial implants (e.g., polymethylmethacrylate, silicone, polytetrafluoroethylene, polyacrylamide, lifting threads) anywhere in the face or neck
- Semi-permanent dermal filler treatment (e.g., calcium hydroxylapatite, poly-L-lactic acid) in the lower face (below the orbital rim)
- Other hyaluronic acid filler materials or collagen-based filler materials below the orbital rim

- Facial tissue augmentation with fat injections, botulinum toxin injections in the lower face (below the orbital rim), mesotherapy, or cosmetic procedures in the face or neck (e.g., face-lift, laser, photo-modulation, intense pulsed light, radio frequency, dermabrasion, moderate or greater depth chemical peel, microneedling, or other ablative procedures)
- Use of any lip plumping products or devices
- Use of any OTC or prescription, oral or topical, anti-wrinkle products for the lips or around the mouth (Subjects who have been on a regimen of such products for at least 90 days are eligible for the study and must continue their regimen throughout the study.)

#### **7.4.7.3 Concomitant Medications and Treatments Allowed During the Study**

Permitted medications/treatments include any concomitant medication/treatment not listed in the exclusion criteria (Section 7.3.2).

#### **7.4.8 Assessment of Compliance**

Administration of the study device by the investigator is documented on the CRF.

### **7.5 Study Schedule**

The visit-by-visit schedule of study activities is provided in Section 2. The timing of each visit is relative to Day 1, which is defined as the day the subject is randomized and first treated.

All visits should be performed within the windows specified on the schedule of study activities. Every attempt should be made to have each subject attend each visit as scheduled. If a subject is unable to attend a visit within the specified window the visit should be scheduled as closely as possible to the applicable window.

### **7.6 Study Procedures**

The schedule of study activities summarizes the study procedures to be performed at each visit. Individual study procedures are described below.

All clinical assessments (LFGS, POL, iGAI, lip function, lip sensation, lip texture, lip firmness, lip symmetry, and lip movement/function evaluations) must be conducted by qualified investigators listed on the Form FDA 1572 who have been delegated these tasks by the principal investigator (PI). The PI may delegate this task only to physicians, physician assistants, or nurse practitioners who have documented training for this protocol and past experience conducting the assessment.

The LFGS, POL, iGAI, lip function, lip sensation, lip texture, lip firmness, lip symmetry, and lip movement/function evaluations are to be performed by a research team member who does not participate in treatment and who is blinded to the treatment assignment (blinded Evaluating Investigator).

To minimize variability of evaluations, the same investigator/sub-investigator should perform these assessments for any given subject and anticipate evaluating the subject at each visit, to the extent possible.

#### **7.6.1 Study Roles**

Each site will designate at least one Treating Investigator and at least one blinded Evaluating Investigator. In addition, one or more members of the study site staff may be designated as unblinded for the purposes of assisting in the management of study device use. Any study staff designated as unblinded should have no direct contact with subjects and may not perform any subject evaluations, assessments or measurements (including vital signs, questionnaires, etc.). Designation of unblinded study staff will be recorded in the Delegation of Authorities Log form.

The Treating Investigator will be responsible for conducting the injections, ensuring that the correct randomized study device is administered in accordance with the protocol and other study instructions. The Treating Investigator will assess subjects and determine the need for touch-up injections. Any AEs brought to the attention of the Treating Investigator will be forwarded to the blinded Evaluating Investigator for final adjudication and documentation.

The blinded Evaluating Investigator will be responsible for assigning grades for the various parameters (LFGS, POL, iGAI, lip function, lip sensation etc.). The blinded Evaluating Investigator will be responsible for recording AEs and determining their severity and relationship to the study device or the injection procedure.

**7.6.2 Study Initiation**

The investigational staff may not enroll any subjects prior to completion of a site initiation visit. This visit will include, but is not limited to, an inventory of study supplies (if present) and a detailed review of the protocol, CRFs, and the investigator’s responsibilities as outlined on Form FDA 1572.

**7.6.3 Written Informed Consent**

The study personnel will review the ICF with each subject and give the subject an opportunity to have all questions answered before proceeding with any study procedures. A copy of the signed ICF will be given to every subject and the original will be maintained with the subject’s records.

**7.6.4 Significant Medical History/Demographic Information**

Medical history and demographic information will be obtained at Visit 1/Day 1. The medical history will include a complete review of all current diseases and their respective durations and treatments. Demographic information will include date of birth, sex at birth, race, ethnicity, and Fitzpatrick skin type (Table 1).

**Table 1. Fitzpatrick Classification Scale**

Skin Type	Skin Color	Characteristics
I	White; very fair; red or blond hair; blue eyes; freckles	Always burns, never tans
II	White; fair; red or blond hair; blue, hazel, or green eyes	Usually burns, tans with difficulty
III	Cream white; fair with any eye or hair color; very common	Sometimes mild burn, gradually tans
IV	Brown; typical Mediterranean Caucasian skin	Rarely burns, tans with ease
V	Dark Brown; mid-eastern skin types	very rarely burns, tans very easily
VI	Black	Never burns, tans very easily

**7.6.5 Physical Examination (Including Vital Signs)**

An abbreviated physical examination including height, weight, and vital signs will be recorded. Vital signs will include sitting blood pressure, temperature, heart rate, and respiratory rate. This physical examination will be performed at Visit 1/Day 1 to determine that the subject is healthy enough to participate in the study.

### **7.6.6 Vision Evaluations**

Subjects will be assessed with Snellen visual acuity, confrontational visual fields, and ocular motility by a trained evaluator. These assessments will be performed prior to any treatment. These assessments will also be repeated 30 minutes following any treatment and at all follow-up visits.

### **7.6.7 Prior and Concomitant Medication/Treatment Review**

Prior medications/treatments, including the necessary washout times, and concomitant medications (including prescription, OTC, and dietary supplements taken and other treatments and cosmetic products used by the subject) will be reviewed with the subject. A record of prior medications/treatments taken or used by the subject within 6 months before signing the ICF and concomitant medications/treatments will be obtained at Visit 1/Day 1. Concomitant medications or treatments will be reviewed with the subject at each study visit and telephone contact.

### **7.6.8 Urine Pregnancy Test and Acceptable Contraceptive Methods**

Women of childbearing potential, in addition to having a negative urine pregnancy test at Visit 1/ Day 1, must be willing to use an acceptable form of birth control during the study. The following are considered acceptable methods of birth control for the purpose of this study: oral contraceptives, contraceptive patches, contraceptive implant, vaginal contraceptive, double barrier methods (e.g., condom and spermicide), contraceptive injection (Depo-Provera®), IUD, hormonal IUD (Mirena®), and abstinence with a documented second acceptable method of birth control if the subject becomes sexually active. Subjects entering the study who are on hormonal contraceptives must have been on the method for at least 90 days prior to the study and continue the method for the duration of the study. Subjects who had used hormonal contraception and stopped must have stopped no less than 90 days prior to Visit 1/Day 1.

### **7.6.9 Lip Fullness Grading Scale**

The LFGS is a 5-point photonumeric rating scale that was developed to objectively quantify the 3-dimensional fullness of the lip. The scale ratings are 0 for very thin, 1 for thin, 2 for moderately thick, 3 for thick, and 4 for full (Carruthers et al, 2008). Photographs illustrating the ratings will be provided to each site. The assessments of overall lip fullness considering both lips together, fullness of the upper lip and fullness of the lower lip will be performed by the Treating Investigator at Visit 1 and by the blinded Evaluating Investigator at each study visit.

### **7.6.10 Perioral Lines at Rest Severity Scale**

The POL is a 4-point rating scale which corresponds to the most severe perioral line attribute when the subject's mouth is at rest with the following ratings (Cohen et al, 2014):

0. None = a mouth with no perioral lines
1. Mild = a mouth with a few shallow perioral lines
2. Moderate = a mouth with some moderate lines
3. Severe = a mouth with many deep lines or crevices

The assessments of overall perioral lines at rest severity considering both lips together, perioral lines at rest severity of the upper lip and perioral lines at rest severity of the lower lip will be performed by the Treating Investigator at Visit 1 and by the blinded Evaluating Investigator at each study visit.

### **7.6.11 Review Inclusion/Exclusion Criteria**

The inclusion and exclusion criteria will be reviewed by the investigator or qualified designee to ensure that the subject qualifies for the study.

### **7.6.12 Evaluation for Touch-up**

The Treating Investigator will evaluate the subject at Visit 2 and determine in consultation with the subject the need for a touch-up treatment.

### **7.6.13 Patient Global Aesthetic Improvement (pGAI) Score**

The pGAI score is a 5-point scale with the following categories:

1. Worse – the appearance is worse than the original condition.
2. No change – the appearance is the same as the original condition.
3. Improved – obvious improvement in appearance from the initial condition. A touch-up might further improve the result.
4. Much improved – marked improvement in appearance from the initial condition, but not completely optimal. A touch-up might slightly improve the result
5. Very much improved – optimal cosmetic result.

The pGAI score will be recorded by the blinded Evaluating Investigator at Visits 2, 3, 4, and 5. Subjects will be asked the question “How would you rate improvement in your appearance compared to your initial condition using the scale below?”

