### **7.6.14 Investigator Global Aesthetic Improvement (iGAI) Score**

The iGAI score is a 5-point scale with the following categories:

1. Worse – the appearance is worse than the original condition.
2. No change – the appearance is the same as the original condition.
3. Improved – obvious improvement in appearance from the initial condition. A touch-up might further improve the result.
4. Much improved – marked improvement in appearance from the initial condition, but not completely optimal. A touch-up might slightly improve the result.
5. Very much improved – optimal cosmetic result.

The iGAI score will be assessed by the Blinded Evaluating Investigator at Visits 2, 3, 4, and 5.

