### **7.6.16 Swelling Assessment**

Swelling will be assessed by the Blinded Evaluating Investigator at Visits 2, 3, 4, and 5 using the 5-point scale with the categories that follow. The blinded Evaluating Investigator should examine both upper and lower lip simultaneously and recall the degree of augmentation originally provided for comparison. The subject should not be specifically questioned regarding swelling but if the subject spontaneously reports it, such information can be used to assist in selection of a grade for swelling.

0: None – No swelling noticeable. Lips appear the same as when originally augmented. Any lip enlargement is due to the implanted product only.

1: Minimal – Slight enlargement of either lip beyond the originally provided augmentation. May or may not be noticeable to the subject but is noticeable to the investigator.

2: Mild – Some enlargement of either lip beyond the original augmentation that is easily noticeable to the subject, but the lips do not appear abnormally large.

3: Moderate – Significant enlargement of either lip beyond the original augmentation. Either lip appears abnormally large.

4: Severe – Any degree of swelling that substantially interferes with lip function such as changes in speech or difficulty eating or drinking.

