**7.7.5 Visit 3/Day 56 ( $\pm 4$  days) and Visit 4/Day 84 ( $\pm 4$  days): Interim Visits at Month 2 and Month 3**

- LFGS assessments
- POL assessments
- pGAI assessment
- iGAI assessment
- Lip function evaluation
- Lip sensation evaluation
- Lip texture evaluation
- Lip firmness evaluation
- Lip symmetry evaluation
- Lip movement/function evaluation
- Vision Evaluation (Snellen visual acuity, confrontational visual fields, ocular motility)
- Assess AEs
- Swelling Assessment
- Assess concomitant medications/treatments
- Subject satisfaction with lips (VAS)
- Collect subject diary card at Visit 3 if dispensed at Visit 2
- Schedule next visit
- Complete CRFs

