### **7.8.3 Other Efficacy Analysis**

Other efficacy analysis include

- pGAI, iGAI, and Swelling Assessment at each scheduled visit,
- percent of subjects with treatment success (responder: upper lips, lower lips LFGS) at Visit 3/Month 2 where responder is defined as a subject with at least a 1-grade increase from baseline on the LFGS post augmentation
- percent of responders (upper lips, lower lips) on the POL severity scale at Visit 4/Month 3 (defined as a subject demonstrating  $\geq 1$ -point improvement, i.e., decrease in severity, from baseline),
- satisfaction with lips VAS at each scheduled visit,

- change from baseline to Visit 4/Month 3 and Visit 5/Month 6 in upper lips, lower lips LFGS.

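### The blinded evaluator records the subject's pGAI and rates the iGAI on the same five-point wording at the same visits, with no rule that the iGAI is completed first

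*Protocol*

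**What the plan says.** Protocol 7.6.13 makes the pGAI the subject's answer to a question: "How would you rate improvement in your appearance compared to your initial condition using the scale below". It then names who writes the answer down: "The pGAI score will be recorded by the blinded Evaluating Investigator at Visits 2, 3, 4, and 5".

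Protocol 7.6.14 gives the other score to the same role at the same visits: "The iGAI score will be assessed by the Blinded Evaluating Investigator at Visits 2, 3, 4, and 5". The five iGAI categories carry the same descriptors as the five pGAI categories. Category 3, for instance, reads "Improved – obvious improvement in appearance from the initial condition. A touch-up might further improve the result" in both sections.

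Protocol 7.6 includes the iGAI among the evaluator's assessments and asks for continuity of rater: "To minimize variability of evaluations, the same investigator/sub-investigator should perform these assessments for any given subject".

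The visit lists in Protocol 7.7.3, 7.7.5, 7.7.7 and 7.7.8 place pGAI immediately before iGAI. Neither document says which of the two is to be completed first.

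On status, Protocol 7.8.3 lists "pGAI, iGAI, and Swelling Assessment at each scheduled visit" under other efficacy. SAP 5.5.3 summarises these variables descriptively by treatment on observed data.

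**The concern.** A rater who has just written down the subject's grade, on the scale the rater is about to use, can be pulled towards it. Because the same evaluator should follow a subject across visits, that person may also remember the subject's earlier grades.

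A reader of the study report will naturally take pGAI and iGAI as a patient's view and a professional's view of the same result. If the second was given in knowledge of the first, part of any similarity between them comes from the procedure. It could not be separated out afterwards, because the plan does not ask for the order or time of the two ratings to be recorded. What is at stake is how much weight two similar tables deserve, not the trial's main conclusion.

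**Working it through.** The documents give no figure for either score, so there is nothing of the plan's own to reproduce. The sample size rests on the change in LFGS and is unaffected.

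**1. The provisions side by side**

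| Item | pGAI (Protocol 7.6.13) | iGAI (Protocol 7.6.14) |
|---|---|---|
| Source of the grade | Subject | Blinded Evaluating Investigator |
| Who records or rates it | Blinded Evaluating Investigator | Blinded Evaluating Investigator |
| Visits | 2, 3, 4, 5 | 2, 3, 4, 5 |
| Scale | Five categories | The same five categories and descriptors |
| Required order | None stated | None stated |

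**2. Safeguards looked for.** I found no rule that the iGAI is completed before the pGAI, that the pGAI is sealed or completed by the subject alone, or that someone else records it. The protocol does limit the subject's input to one evaluator grade. For swelling, 7.6.16 says "The subject should not be specifically questioned regarding swelling" and explains how spontaneous reports may be used. Nothing comparable covers the iGAI.

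**3. Possible effect on agreement (assumed values).** Let P be the subject's grade and I the grade the evaluator would give unaided, both with unit variance and correlation r. Suppose the recorded iGAI is (1 − w)I + wP. Its correlation with P is

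[(1 − w)r + w] / √[(1 − w)² + w² + 2w(1 − w)r].

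With r = 0.4:
- w = 0.2: 0.52 / √0.808 = 0.58
- w = 0.3: 0.58 / √0.748 = 0.67
- w = 0.5: 0.70 / √0.700 = 0.84

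Over a wider range of r:

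| r | w = 0.25 | w = 0.5 |
|---|---|---|
| 0.3 | 0.55 | 0.81 |
| 0.5 | 0.69 | 0.87 |
| 0.7 | 0.82 | 0.92 |

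Neither r nor w comes from the documents, and linear mixing is a simplification for a five-category grade. The figures show direction only.

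**4. Possible effect on the comparison of arms.** Under the same model, with w equal in both arms because subject and evaluator are blinded, the arm difference in recorded iGAI is (1 − w)D_I + wD_P. Here D_I and D_P are the arm differences in the evaluator's unaided grade and in the subject's grade. The result lies between two blinded differences, so nothing in the mechanism pushes it towards PN40082 or towards the comparator.

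**5. Reach.** The primary endpoint (Protocol 7.8.1, SAP 5.5.1) and the secondary endpoints (Protocol 7.8.2, SAP 5.5.2) use LFGS and POL only. SAP Tables 14.2.3.1 and 14.2.3.2 show pGAI and iGAI as separate frequency tables. No agreement statistic, correlation or joint success rule is planned.

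**The case against.** The strongest reply is that the harm has no object in the plan. Neither document calls the two scores independent, neither analyses them together, and both are descriptive. Two ratings of the same lips would correlate under any procedure. This stands, and it limits the point to how the scores are obtained.

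Second, a list is not a sequence. The Schedule of Activities puts the swelling assessment between pGAI and iGAI, while the visit lists place swelling later, so the documents do not follow one order. This also stands. The point therefore rests on the recorder named in 7.6.13 and on the absence of an ordering rule. The CRFs are not among the documents and might already set a page order.

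Third, 7.6.13 does not say who puts the question, and a question that refers to a printed scale is compatible with a form shown to the subject. That is fair, but the evaluator is still the named recorder.

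Fourth, the comparator's own studies, as described in its instructions for use, had investigators and subjects rate on a common improvement scale. That is precedent for a shared scale. It does not show that the rater should also record the subject's answer.

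Two stronger readings are tempting and are not supported:
- A reader might infer that the influence flatters PN40082. Protocol 7.4.4 blinds both subject and evaluator, and step 4 of the working shows no direction.
- A reader might infer that the satisfaction VAS is already a subject-completed form, so that the pGAI is the exception. Protocol 7.6.23 says only that subjects are asked to assess their satisfaction on the scale. It does not say who makes the mark.

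**Conclusion.** The procedure allows the evaluator's iGAI to be influenced by the subject's pGAI, so the two scores are not independently obtained. This is a possibility left open by the text, not a demonstrated effect.

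Its importance is low. It touches two descriptive outcomes, changes no sample size, power or error rate, and leaves every primary and secondary conclusion as it is. The view that it need not favour either arm assumes that the blinding of subject and evaluator holds. The correlation figures rest wholly on assumed inputs and should not be read as estimates. The point is worth making because the remedy costs almost nothing.

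**What to change.** State in Protocol 7.6.13, 7.6.14 and the visit lists (7.7.3, 7.7.5, 7.7.7, 7.7.8) that, whenever these assessments are done at a visit, the evaluator completes and signs LFGS, POL and iGAI before the pGAI is obtained. Including LFGS and POL extends the same protection to the primary endpoint. They are already listed ahead of pGAI, but that order is not mandated.

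Preferably, have the subject complete the pGAI on a form. Fixing the order deals with the current visit only. If another blinded staff member collects the form, the evaluator also does not carry the subject's earlier grades forward to later visits.

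The cost is protocol wording and the order of CRF pages. No visit, procedure or analysis is added.
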